9.5 Follow-up

All follow-up assessments will be performed over the phone. Follow-up assessments will occur at 30, 60, and 90 days post enrollment.

Follow-up assessments will include:

- 1) Attitudes toward Pre-Exposure Prophylaxis Scale (APS) (Appendix 3)
- 2) Section 4 of ICAP "Screening for Substantial Risk of HIV" (Appendix 5)
- 3) Satisfaction questionnaire and qualitative assessment and visit specific satisfaction instrument (VSQ-9) (Appendix 6)
- 4) Adherence information measured by (1) self-report. Self-report will be assessed with the single measure Guidelines Regimen Information Program (GRIP) guide and questions on last dose and number of missed doses since prior follow-up. (Appendix 7)
- 5) CDC Sexual Behavior Questions (CSBQ) (Appendix 4)
- 6) STAR*D PRISE (Side-effect assessment)

Assessment of engagement in PrEP care at 30, 60, and 90 days post enrollment will be verified by direct contact with the treatment provider/program provided or by EMR review if the patient is linked within the Mount Sinai Health System. If the patient is receiving their PrEP care outside of the Mount Sinai Health System, a signed release authorization form will be sent.

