11.0 DATA MANAGEMENT AND STATISTICAL ANALYSES

11.1 Statistical Analysis

11.1.1 General approach

Nominal and ordinal categorical variables will be summarized as frequencies and percentages. Continuous variables will be summarized with the following descriptive statistics: N, mean, standard deviation, median, minimum, maximum, interquartile range, and range.

No imputation of missing data will be performed for any of the analysis given the pilot nature of the study and small sample size.

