11.1.2 Analysis of Primary and Secondary Outcomes

Analysis will be on an intention-to-treat basis. In statistical analyses, participants will be included to the date of their last active follow-up visit. Comparisons between control and experimental (iPrEP) arms. To assess the success of randomization, a summary of the baseline variables by treatment group will be tabulated and univariate comparisons performed. The primary outcome, retention in care and PrEP usage, will be compared with proportions and Fisher's exact derived confidence intervals. Secondary outcomes: Secondary analysis will focus on determining how retention in care, risk behavior, adherence or STI diagnosis differ between the groups at any of the follow-up time points. PrEP adherence based on pill counts will be calculated by dividing the number of pills taken by the number of pills prescribed. Adherence will be calculated by study month for each participant. Group adherence comparisons will be compared using Wilcoxon rank sum test. Retention in care, STI diagnosis and risk behavior at each time point will be analyzed for each study visit. Retention in care and STI diagnosis will be treated as dichotomous variables for analysis. Measures of risk behavior will include consistency of condom use and number of sexual partners since prior study visit. Condom use will be treated as an ordinal variable and number of sexual partners as a continuous variable for analysis.

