17.2 Trial Safety

Events that would preclude a participant from continuing the intervention:

Safety concerns: Guidelines published by the Centers for Disease Control and Prevention (CDC) provide clear guidance for clinicians prescribing emtricitabine/tenofovir disoproxil fumarate or emtricitabine/tenofovir alafenamide for pre-exposure prophylaxis (PrEP). Indications for not starting or stopping PrEP once started would include renal insufficiency (eCrCL of ≤ 60 ml/min), HIV infection, Hepatitis B, pregnancy, signs or symptoms of acute HIV infection, possible HIV exposure within the last 72 hours. Indications for stopping PrEP would be a new HIV or Hepatitis B infection, worsening renal function, intolerable side effects, hypersensitivity reaction, osteopenia or pregnancy. In the group of patients randomized to iPrEP if any these safety concerns arise during the 14 days the patient is taking the PrEP starter pack they will be addressed by the PI and the patient will be withdrawn from the study since they will no longer be considered PrEP eligible.

Participants could also be removed from the study by the investigator if they do not complete any follow-up assessments within 90-days of enrollment.

Managing any medication related issues: In the group of patients randomized to iPrEP medication related side-effects that occur while the patient is taking the 14-day starter pack will be addressed by the PI. After 14-days or linkage to care (whichever occurs first) the treating PrEP provider will manage the patient as clinically indicated. For any medication related emergency we will provide a "study card" with a number to call to speak with a physician and inform patients if they need immediate treatment to go to the closest emergency room. There is no wash-out period. Patients will told to inform their treating provider of any other medications they are taking including any over-the-counter medicines. For those patients who wish to discontinue PrEP, we will recommend a test to determine HIV status at the time of discontinuation. We will also enquire about the reason for PrEP discontinuation, recent medication adherence and reported sexual risk behavior.

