18.4 Adverse Event Reporting

Appropriately qualified and trained personnel will elicit participant reporting of AEs and SAEs (Appendix 10) at each follow-up assessment. Study personnel will obtain as much information as possible about the reported AE/SAE to complete the AE/SAE forms and will consult with the PI as necessary.

Standard reporting, within 7 days of the site becoming aware of the event, will be required for all AEs. Expedited reporting (within 24 hours of their occurrence and/or site's knowledge of the event) is required for reportable SAEs.

Reportable adverse events will be followed until resolution, stabilization or study end.

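### iPrEP participants with an on-drug safety concern in the first 14 days are withdrawn from the study, not only from PrEP, and may leave the primary-outcome denominator

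*Combined protocol and SAP*

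**What the plan says.** **Withdrawal rule.** Section 17.2 lists reasons to stop PrEP once begun: new HIV or hepatitis B infection, declining kidney function, intolerable side effects, hypersensitivity, osteopenia and pregnancy. If such a concern, or one of the reasons not to start, arises in an iPrEP participant during the 14 days of the starter pack, the PI deals with it and "the patient will be withdrawn from the study since they will no longer be considered PrEP eligible". For the later period the same section says: "After 14-days or linkage to care (whichever occurs first) the treating PrEP provider will manage the patient as clinically indicated". It attaches no study withdrawal to that.

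**Neighbouring text.** Section 9.3 says that for side effects in the same 14 days the patient and the PI discuss whether to carry on with PrEP or stop it. Section 18.9 leaves it to the PI whether an adverse event calls for withdrawal from study medication. Section 9.3 also ends participation, in either arm, when a contraindication is found. Section 12.5 does the same for a positive pregnancy test.

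**Follow-up.** Section 9.5: "Follow-up assessments will occur at 30, 60, and 90 days post enrollment". The primary outcome (Engagement in Treatment Survey, Section 10.5.1) starts from what the participant reports at those contacts and is then confirmed with the provider or the record. Under Section 18.4, trained staff "will elicit participant reporting of AEs and SAEs (Appendix 10) at each follow-up assessment". The same section adds: "Reportable adverse events will be followed until resolution, stabilization or study end".

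**Analysis.** Section 11.1.2: "Analysis will be on an intention-to-treat basis". Its next sentence says that "participants will be included to the date of their last active follow-up visit". Section 11.1.1: "No imputation of missing data will be performed for any of the analysis".

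**The concern.** Stopping the drug and leaving the study are different events, and Section 17.2 joins them. It does so in one arm only, for a reason caused by the treatment, in people whose status on the primary outcome is probably already known: they have stopped PrEP.

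A control participant who starts PrEP at a clinic and cannot tolerate it stays in follow-up. So does an iPrEP participant with the same reaction on day 20. An iPrEP participant with that reaction on day 10 does not.

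If those early stops drop out of the denominator instead of counting as non-use, 90-day usage in the iPrEP arm is overstated. That figure, and the arm's attrition rate, are what the pilot exists to supply for the definitive trial (Aim 1b, Section 4.0). The trial would also lose these participants' day-90 HIV, STI and risk-behavior data, and the routine adverse-event questions asked at each call.

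**Working it through.** **1. Does the rule mean the study or the drug?** The list in Section 17.2 is introduced as events that bar a participant from continuing the intervention, which suggests the drug. The operative sentence says study. The next paragraph, on people who complete no follow-up, says they could also be removed from the study, which treats the preceding rule as study removal. Sections 9.3 and 18.9 speak of the drug only. The literal reading is study withdrawal, and staff have conflicting instructions.

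**2. What is lost?** Withdrawal happens by day 14. The calls are at days 30, 60 and 90. Calls completed before withdrawal: 0 of 3. Calls lost: 3 of 3.

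**3. How are they counted?** Someone with no follow-up visit has no last active visit at which to be included. No section classes a documented stop as non-use, and none says such a person is excluded. The denominator is undetermined.

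**4. The plan's own figure.** Section 11.1.3 gives a power table for 40 against 40. Exact enumeration of the two-sided pooled Z test at 0.05 reproduces all seven values to four decimals (for example 0.4581 at 50% against 70%). The table is not in dispute. It fixes the intended denominators at 40 per arm.

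**5. Size if early stops leave the denominator.** Inputs: 40 per arm and 50% control usage (Section 11.1.3). Assumptions: equal true usage of 20/40 in both arms; w iPrEP participants stopped under Section 17.2, none using PrEP at day 90. The documents give no rate for w, so 1, 2 and 4 of 40 (2.5%, 5%, 10%) are illustrations. Observed iPrEP usage = 20/(40 − w).

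| w | iPrEP usage | Shift (points) | Rejection rate, pooled Z | Rejection rate, Fisher |
|---|---|---|---|---|
| 0 | 20/40 = 50.0% | 0 | 5.7% | 3.3% |
| 1 | 20/39 = 51.3% | +1.3 | 4.5% | 4.4% |
| 2 | 20/38 = 52.6% | +2.6 | 6.0% | 4.8% |
| 4 | 20/36 = 55.6% | +5.6 | 7.8% | 6.3% |

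The rejection rates are exact, with control binomial (40, 0.5) and iPrEP binomial (40 − w, 20/(40 − w)). With 28 iPrEP users the rates would be 28/39 = 71.8%, 28/38 = 73.7% and 28/36 = 77.8% instead of 70.0%.

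**6. Variations at w = 2.**
- Two more leave each arm for contraindications: 20/36 − 20/38 = +2.9 points.
- One control and no further iPrEP participant leaves: 20/38 − 20/39 = +1.3 points.
- One of the two stopped participants restarts by day 90: 19/38 = 50.0%, shift 0.
- Both are kept as non-users: 20/40 = 50.0%, shift 0.

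**7. Against the pilot's precision.** The 95% half-width for the difference at 50% usage is 1.96 × √(0.25/40 + 0.25/40) = 0.219, or about 22 points.

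**The case against.** **Intention-to-treat already answers it.** Section 11.1.2 names the principle, which ordinarily keeps everyone randomized. Counting a documented stop as non-use draws on an observed fact, so the bar on imputation does not forbid it. This stands in part: a reader might infer that the plan excludes these participants, and the documents do not say that. They leave the matter open, and the sentence on the last active visit pulls the other way. The same gap affects anyone without a day-90 report. At the 85% follow-up expected in Section 17.2, that is 0.15 × 40 = 6 per arm, probably more than the early safety stops. The early stops differ because the protocol itself creates the loss, in one arm.

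**The safety data are not lost.** A reader might infer that these adverse events go unfollowed. They do not: the PI handles the event, and reportable events are followed to resolution, stabilization or study end. Section 18.9 also asks voluntary early withdrawals in the iPrEP arm for an end-of-medication visit, and Section 17.2 asks people who wish to discontinue about reasons, adherence and risk behavior. These collect data around the stop. They do not supply day-90 usage or ask about later events.

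**The effect is small and its rate assumed.** This stands. One or two stops move usage by 1.3 to 2.6 points against an interval of about ±22, and the Fisher rejection rate stays below 5%. The +5.6 needs an assumed 10% stop rate with no restarts. Section 11.1.3 already disclaims definitive efficacy.

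**A blanket retention rule would create the opposite bias.** This stands and shapes the fix. The Section 17.2 list also covers hepatitis B, renal, HIV and pregnancy findings, and baseline results are expected within 48 hours of discharge (Section 9.3), inside the 14 days. If iPrEP participants with such results stayed in while controls left under Section 9.3, two cases per arm would give 20/40 = 50.0% against 20/38 = 52.6%, a −2.6 point artefact.

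**Conclusion.** The concern holds in a limited form. Read literally, Section 17.2 removes iPrEP participants with an early on-drug safety concern from the study, has no counterpart for controls or for later events, conflicts with Sections 9.3 and 18.9, and costs all three outcome calls. Loss from the denominator is possible, not certain. If it occurs, and the stopped participants are not using PrEP at day 90, iPrEP usage is overstated by 1.3, 2.6 or 5.6 points at an assumed 1, 2 or 4 stops of 40 with 20 users. If intention-to-treat is applied strictly, the shift is zero.

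The change should be made because the loss is tied to treatment and avoidable at little cost. The documents do not support a claim that the primary comparison is seriously biased. Whether PrEP should be stopped in these patients is not in question.

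**What to change.** In Section 17.2, replace the study-withdrawal clause with:

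> If intolerable side effects, hypersensitivity or another safety concern newly arising on PrEP occurs during the 14 days, PrEP is stopped; the participant stays in the study for the day 30, 60 and 90 calls, AE/SAE elicitation and record review unless consent is withdrawn. Contraindications found on samples taken before randomization (including HBV, renal function, HIV and pregnancy) are handled under Sections 9.3 and 12.5 identically in both arms.

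In Section 11.1.2, add:

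> Participants who stop PrEP for an on-drug event stay in their randomized arm and count as not using PrEP at day 90 unless use is reported.

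The exception for pre-randomization samples must be in the inserted text itself, to avoid the reverse artefact. Sections 9.3 and 12.5 need no change. The side-effect questionnaire is given only to patients taking PrEP (Section 10.5.7), so later events in stopped participants would come from the AE/SAE questions.

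**Cost.** A minor protocol amendment with IRB review and possibly consent wording, plus, per affected participant, up to three already scheduled calls and 3 × $25 = $75 in compensation (Section 9.6). For 1 to 4 participants that is $75 to $300. The downside is a few calls to people no longer on PrEP.

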Patients will be instructed at the time of discharge that they will be contacted by a member of the PrEP Warm Line to schedule follow-up with a PrEP provider. The decision to start PrEP for those not randomized to the iPrEP arm or to stop or continue PrEP for those randomized to the iPrEP arm will be a decision made by the patient in conjunction with their PrEP provider. The ED clinical team will be available to assist patients should have they have any concerns or problems before that linkage occurs. For those randomized to the iPrEP arm if they have any side-effects within the first 14-days of starter pack use they will contact the study team and a decision to continue or stop PrEP will be made after a discussion between the patient and the PI. All patients enrolled in the study will receive standard PrEP counseling which includes information about the need for frequent HIV testing and risk reduction strategies. The importance of follow-up with the PrEP provider will be stressed. We do not anticipate the need for any re-testing (HIV, LFTs, eCrCL) by the study team after ED discharge. These tests are not typically recommended until the patient has been on PrEP for at least 30 days and sometimes not until 90-days. All recommended follow-up testing will be the responsibility of the clinical PrEP provider.

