18.9 Participant Withdrawal

The PI will apply his/her judgement to determine whether or not an adverse event is of sufficient severity to require that the participant be withdrawn from further study medication. A participant may also voluntarily withdraw from treatment due to what he/she perceives as an intolerable adverse event or for any other reason. If voluntary withdrawal is requested within the first 14-day and the patient was assigned to the iPrEP arm, the participant will be asked to complete an end-of-study medication visit to return unused medication and document end-of-medication outcomes.

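### Section 17.2 takes iPrEP participants out of the study, not just off the drug, for tolerability events in the 14 starter-pack days; controls have no matching rule

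*Combined protocol and SAP*

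**What the plan says.** The sentence at issue stands in Section 17.2, under a lead-in about "Events that would preclude a participant from continuing the intervention". After a list of reasons not to start or to stop, the section gives on-treatment reasons: "Indications for stopping PrEP would be a new HIV or Hepatitis B infection, worsening renal function, intolerable side effects, hypersensitivity reaction, osteopenia or pregnancy". It then turns to patients "randomized to iPrEP if any these safety concerns arise during the 14 days the patient is taking the PrEP starter pack". The PI addresses the concern, and "the patient will be withdrawn from the study since they will no longer be considered PrEP eligible". The sentence names one arm and one window. After 14 days or linkage to care, whichever is earlier, "the treating PrEP provider will manage the patient as clinically indicated".

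Other sections handle the same kind of event as a drug decision:
- Section 9.3, on side effects during the starter pack: "a decision to continue or stop PrEP will be made after a discussion between the patient and the PI".
- Section 18.9: the PI judges whether an adverse event is of "sufficient severity to require that the participant be withdrawn from further study medication".
- Appendix 10, adverse event report, item 4a: permanent drug stop and termination from the study are separate options.

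For controls, Section 9.3 leaves the decision to start PrEP to the patient and the outpatient provider. Two exits apply to both arms: a contraindication found on the laboratory work-up (Section 9.3) and pregnancy found on urine testing (Section 12.5).

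On analysis, the primary outcome is PrEP use at 90 days (Section 2.0) and calls take place at days 30, 60 and 90 (Section 9.5). Section 11.1.2 states intention-to-treat but includes participants only up to their last active visit, and Section 11.1.1 rules out imputation.

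**The concern.** Stopping PrEP because it is not tolerated is close to being the primary outcome itself, since such a person is likely not to be using PrEP at day 90. A rule that ends study participation for that reason, in one arm only and before any outcome call, would tend to take failures out of the experimental arm's denominator. A control who starts in clinic and stops for nausea stays in follow-up and counts as a non-user; an iPrEP participant who stops for intolerable nausea on day 7 may not be counted at all.

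Two products of the trial are exposed: the comparison of 90-day use, and the attrition rate that Aim 1b collects to plan the definitive trial. Section 17.2 itself, under data management, names loss to follow-up as the main threat to validity.

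**Working it through.** **1. Which triggers are one-armed?** Taking the reasons in 17.2 in turn:
- HIV, hepatitis B or reduced creatinine clearance on enrollment labs: Section 9.3 ends participation in either arm. Not one-armed.
- Pregnancy on urine testing: Section 12.5 has no arm restriction. Not one-armed.
- New HIV infection or worsening renal function within 14 days: Section 9.3 expects no retesting by the study team after discharge, so these are unlikely to surface through the study.
- Osteopenia: Section 12.2 describes it as a risk of long-term use, so it is not a realistic 14-day event.
- Intolerable side effects and hypersensitivity: no equivalent exit for controls. These are the substance of the imbalance.

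**2. Timing.** The window closes at day 14 and the first call is at day 30, a gap of 30 − 14 = 16 days. Anyone withdrawn under the rule leaves before any outcome call.

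**3. Inputs.** 40 per arm and 50% use in controls come from Section 11.1.3. The power table there reproduces to four decimals by exact enumeration of the two-sided pooled Z test (for example 0.4581 for 50% v 70% and 0.6474 for 50% v 75%) and is not in dispute. The plan gives no figure for withdrawals under 17.2. The number removed, k, is therefore an assumption: 1 or 2 of 40, with 4 as a stress case.

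**4. Formula.** Let u be the true number of iPrEP users among 40.
- k non-users removed: observed rate = u / (40 − k).
- k users removed: observed rate = (u − k) / (40 − k).

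**5. No true effect (20/40 in each arm).**
- Non-users removed: 20/39 = 51.3% and 20/38 = 52.6%, so spurious differences of +1.3 and +2.6 points. Stress case: 20/36 = 55.6%, or +5.6.
- Users removed: 19/39 = 48.7% and 18/38 = 47.4%, so −1.3 and −2.6 points.

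**6. True use 30/40 (75%) against 50%, a true difference of 25 points.**
- Non-users removed: 30/39 = 76.9% and 30/38 = 78.9%, so the difference shows as 26.9 or 28.9 points.
- Users removed: 29/39 = 74.4% and 28/38 = 73.7%, so 24.4 or 23.7 points.

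**7. Attrition.** Each removal adds 1/40 = 2.5 points in the iPrEP arm only.

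**8. Yardsticks.** The 95% half-width for 75% v 50% at 40 per arm is 1.96 × √(0.75×0.25/40 + 0.5×0.5/40) = 1.96 × 0.1046 = 20.5 points. The follow-up of about 85% expected in 17.2 implies 0.15 × 40 = 6 ordinary losses per arm.

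**The case against.** The strongest reply is that the plan already leans towards stopping the drug only. Sections 9.3 and 18.9 and Appendix 10 all contemplate it, and a later paragraph of 17.2 has the PI deal with starter-pack side effects without mentioning withdrawal. This stands as far as it goes: the defect is partly an inconsistency. But nothing cancels the withdrawal sentence, so staff have two instructions for one event.

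The second reply is that data loss is inferred. Section 18.9 asks iPrEP participants who withdraw voluntarily in the first 14 days for an end-of-medication visit, 17.2 asks about reasons and adherence when a patient wishes to discontinue, and 18.4 follows reportable events. No section says that withdrawn participants leave the denominator. This is fair, and it is why the loss is only likely. None of these provisions yields PrEP use at day 90, however, and no rule counts the withdrawn as non-users.

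The third reply is size: at 1 or 2 removals the shift is small beside sampling error and ordinary losses, in a pilot that Section 11.1.3 calls underpowered. That also stands. The difference is that this loss is written into the plan, falls on one arm and is tied to the outcome.

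Stronger readings that the documents do not support:
- A reader might infer that every trigger in 17.2 acts on iPrEP alone. Pregnancy on urine testing and laboratory contraindications do not.
- A reader might infer that an exposure reported while on the starter pack ends participation, because the first list includes "pregnancy, signs or symptoms of acute HIV infection, possible HIV exposure within the last 72 hours". The withdrawal sentence points to neither list, and the first can be read as entry barriers recognized late. This is loose drafting and no part of the point.
- A reader might make much of Fisher p-values: 28/40 v 20/40 gives 0.110, and dropping two non-users gives 0.038. The count is assumed and the trial is not meant to be decisive, so this settles nothing.

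**Conclusion.** The concern holds for on-treatment tolerability events in the first 14 days. If 17.2 is followed as written, iPrEP participants with intolerable side effects or hypersensitivity leave the study before any outcome call and would probably have no 90-day outcome, despite the intention-to-treat statement.

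The likely effect is an iPrEP estimate that is slightly too high: 1.3 or 2.6 points with no true effect and 1 or 2 non-users removed. This rests on three assumptions: the count, that those removed would not be using PrEP at day 90, and that no outcome is obtained after withdrawal. The plan does not establish that the result must favor iPrEP. A participant withdrawn early could restart through a clinic, and if those removed were users the sign would reverse. It is a modest flaw, worth correcting because the remedy is cheap and the definitive trial could inherit the rule.

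**What to change.** In Section 17.2, state that intolerable side effects, hypersensitivity or another on-treatment stopping reason during the starter pack stops study drug only. The participant stays in the 30-, 60- and 90-day calls and in the intention-to-treat analysis at day 90 with actual PrEP use. PI management of the event is unchanged.

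So that the sections agree, either extend the same follow-up rule to randomized participants covered by the contraindication exit in 9.3 and the pregnancy exit in 12.5, or state that those both-arm exits remain as they are. Amending 17.2 alone would leave it at odds with them. The recent-exposure item needs no change for this purpose.

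The cost is a short wording amendment with IRB review. The calls are already scheduled for every participant, so no new procedure or staff is needed.
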